2. STUDY PROCEDURES

a. Procedures

Unite Here Health will institute a novel program focused on providing patients with a lay health coach who will engage patients with goals of care after a diagnosis of cancer. Unite Here Health will enroll patients into the study after a new diagnosis of cancer or after a diagnosis of cancer that has progressed to a worsening stage. Unite Here Health staff will identify patients for the program through primary care physicians, oncologist referrals, and hospitalization daily notice of admissions and emergency department reports which Unite Here Health routinely receives as part of usual care. Patients without capacity to consent verbally will not be eligible for the study.

The Unite Here Health staff will contact eligible patients by telephone to introduce the study. If the patient is interested, he/she will be randomized into the usual oncology care arm versus the lay health worker intervention arm. Patients randomized into the intervention will be assigned a lay health worker who will contact the patient to begin the intervention. The intervention includes: education on early advance care planning,

documenting goals of care, assessing symptoms, and coordinating community services (such as home health, home visits, and home hospice).

The Unite Here Health staff, as part of their usual assessments, will conduct the following assessments for patients enrolled in the intervention and the usual oncology care arm at time of randomization and at 6 and 12 months after enrollment: a satisfaction with decision-making survey to compare changes in satisfaction, a patient activation measure survey (PAM survey), and the Functional Assessment of Cancer Therapy - General quality of life survey. At these time points, additional data collected as part of usual care will also be assessed for each patient. This includes: healthcare utilization (total number of emergency department visits and hospitalizations, referral to palliative care, and hospice receipt). This data will be abstracted from the patients' claims data that Unite Here Health routinely reviews and collects.

b. Procedure Risks

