5. RISKS

a. Potential Risks

As part of the study, patients will receive either usual care or will be assigned into the intervention. Patients assigned to the intervention will receive a lay health coach assigned to educate patients in goals of care, assist with symptom assessments, and coordinate community care (such as home hospice, home health services). All patients in the study will receive 3 surveys at baseline, 6 and 12 months after study enrollment: satisfaction with decision, patient activation, and quality of life assessment. receive satisfaction

surveys with their care (CAPHS-G). These will be anonymous surveys and will not be linked to the patient.

b. Procedures to Minimize Risk

We will not obtain identifiable records. For analysis purposes, all patients enrolled into the study will be assigned a unique identifier number. Data will be provided to the Stanford PI in aggregate. Patients will be coded and no direct identifiers will be linked to the patient. All data will be kept in a secure REDCAP database without any patient identifiers other than a unique identifier code.

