Appendix 1: Patient Procedures

Stanford –CareMore-Oncology Institute of Hope and Innovation- Lay Health Worker Symptom Assessment Quality Improvement Pilot

Identifying Patients

- ❖ All patients with newly diagnosed cancer Stage 3 or 4 or hematologic malignancies requiring Medical Oncology will be included in the program.
- 1) Patients will be categorized as either "High Risk" or "Low-Risk" based on the following criteria:
- 1) High Risk: All metastatic cancer patients as well as all patients on active chemotherapy, all patients with symptom scores 4 or above, or any change in symptom of greater than 2 points from prior assessment
- 2) Low Risk: Patients who are not on chemotherapy and are undergoing routine follow-up/surveillance, who have no symptom scores of 4 or above, and no change in symptom scores
- 3) Three months after a non-metastatic patient has completed adjuvant chemotherapy or treatment, he/she will be transitioned to low-risk status unless trigger event occurs as above.

Patient Engagement

- LHW will contact all patients via telephone who meet the criteria prior to their first oncology appointment
- LHW will schedule an initial oncology consultation appointment with the patient within 5 days of initial contact
- LHW will discuss program
- LHW will prepare the patient for their upcoming initial consultation with an oncologist
- LHW will invite and encourage the patient to include anyone in the conversation such as family/caregiver and encourage the patient to include anyone who may potentially be attending future oncology appointments with the patient.
 - If necessary, the LHW will offer to reschedule the call to accommodate patient's request for others to be present during conversation.
- LHW will provide contact information for patients to use in the event of any future triggers and provide a list of all the appropriate triggers to the patient and the care circle.
 - Triggers Include:
 - Disease progression
 - Unexpected side effects
 - Potential change of treatment
 - ED visit or hospital use
 - If for any reason patient does not feel comfortable
 - Life situation changes in a manner that potentially impacts symptoms
 - Oncologist refers patient back to the LHW
 - Patient family members need education/clarification/support

Introduction of HVCCP

- ❖ Explain the purpose is to help patients maintain symptom relief.
 - The LHW is here to support the patient throughout this process

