- ❖ Identify symptom control resources, which the oncologist may later prescribe as appropriate (including palliative care resources).

- Note: Here is a good place to address palliative care and begin the intake/ESAS. In addition, connect the patient with individual and group-based opportunities (support groups at the Cancer Institute) for emotional support involving interaction with trained professionals and other people undergoing similar health challenges
- ❖ Invite and encourage the patient to include anyone in the conversation such as family/caregiver and encourage the patient to include anyone who may potentially be attending future oncology appointments with the patient. Ask patient “are there any members of your family that you think will be part of your care?”
 - Note: If necessary, offer to reschedule the call to accommodate patient’s request.
- ❖ Provide ESAS for baseline assessment

Prior to each patient’s first oncologist appointment:

Educational Materials

- ❖ LHW will discuss educational materials such as videos/handouts with patients
- ❖ All cancer patients will be educated on the general topics of chemotherapy, radiation, and surgical approaches to treating cancer and potential side effects.
- LHW will discuss available handouts and reading materials with patients during the initial phone conversation
 - Front office staff will provide patients with handouts for their specific diagnosis, chemotherapy and symptom management (constipation, diarrhea, nausea, etc.) upon check out

Edmonton Symptom Assessment System (ESAS)

- 1) During the initial phone conversation the LHW will screen patients for symptom management using Edmonton Symptom Assessment System (ESAS) tool (attached)
- 2) After the initial consultation, LHW will review patient list with Physician Assistant to determine patient risk stratification and will contact and screen all high-risk patients via telephone on a weekly basis and all low risk patients on a monthly basis
- 3) LHW will input data into Rabbit EHR via ESAS/PHQ-9 template
- 4) Physician Assistant will review findings of ESAS results through EHR and if patient scores 4 or higher PA will notify the treating oncology practitioner and initiate usual care process for identified symptom management
- 5) Treating oncology practitioner must review/treat and agree with appropriate orders for any positive findings noted on the ESAS

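### Appendix 1 triggers lay health worker contact and ESAS screening by diagnosis and risk group, Sections 2a and 5a by randomization, and the protocol does not say which arm the Appendix governs

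*Protocol*

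**What the plan says.** Section 2a of the protocol sets an order of events. First, "The Unite Here Health staff will contact eligible patients by telephone to introduce the study". An interested patient is then allocated: "he/she will be randomized into the usual oncology care arm versus the lay health worker intervention arm". Only after that does the lay health worker (LHW) appear: "Patients randomized into the intervention will be assigned a lay health worker who will contact the patient to begin the intervention". Besides education on advance care planning, the intervention consists of "documenting goals of care, assessing symptoms, and coordinating community services (such as home health, home visits, and home hospice". Section 5a repeats the restriction by arm: "Patients assigned to the intervention will receive a lay health coach assigned to educate patients in goals of care, assist with symptom assessments". Section 2g names ESAS at 12 months as the primary endpoint.

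Appendix 1 describes entry differently. Under Identifying Patients, everyone with newly diagnosed Stage 3 or 4 cancer or "hematologic malignancies requiring Medical Oncology will be included in the program". Under Patient Engagement, "LHW will contact all patients via telephone who meet the criteria prior to their first oncology appointment". The Appendix then has the LHW raise palliative care and support groups, take a baseline ESAS in the initial call, and screen high-risk patients weekly and low-risk patients monthly. On education it says "All cancer patients will be educated on the general topics of chemotherapy, radiation, and surgical approaches to treating cancer and potential side effects".

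**The concern.** The two parts of the protocol use different triggers for the same act. In the body, an LHW contacts a patient because of allocation; in the Appendix, because of diagnosis. The Appendix mentions neither randomization nor arms. Staff working from it alone would have no instruction to leave usual-care patients out, and none to wait until a patient has been randomized.

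The trial compares LHW support with usual oncology care. Symptom assessment is a named part of the intervention, and the Appendix passes ESAS scores of 4 or higher on to the treating practitioner. That component therefore bears directly on the primary endpoint. If it reached the usual-care arm, the difference between arms would shrink, and a null result could not be told apart from contamination. Analysis afterwards could not restore the lost contrast.

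**Working it through.** The protocol states no power, effect size, standard deviation, allocation ratio or dropout rate, and it supports the enrollment of 180 by feasibility alone (Section 4a). There is no figure to reproduce, so the check is mainly a comparison of texts.

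**Step 1. Trigger, caller and follow-up.**

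| Point | Sections 2a and 5a | Appendix 1 |
|---|---|---|
| First call made by | Unite Here Health staff | LHW |
| LHW contact triggered by | Allocation to the intervention | Meeting clinical criteria |
| Timing of LHW contact | After randomization | Before the first oncology visit; randomization not mentioned |
| Continuing LHW contact | Intervention arm | All patients, weekly or monthly by risk group |
| Usual-care branch | Yes | None |

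The rows conflict on their plain wording. No sentence in either part says that the Appendix is confined to the intervention arm.

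**Step 2. Which Appendix activities are intervention components under Section 2a.**

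- Symptom assessment: listed in Section 2a, and done by the LHW with ESAS in the Appendix. Clear overlap.
- Palliative care and support-group linkage: close to the community services in Section 2a. Arguable overlap.
- Scheduling the consultation, preparing the patient for it, and education on chemotherapy, radiation and surgery: not listed in Section 2a. These cannot be called components reserved for the intervention arm.

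**Step 3. Who could be reached.** Sections 4a and 4f admit any newly diagnosed cancer and any relapse or progression. The Appendix covers new diagnoses that are Stage 3 or 4 or hematologic. Even applied literally, it would not reach relapsed or progressing patients or newly diagnosed earlier-stage solid tumors. The documents do not say what share of the usual-care arm would remain.

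**Step 4. Size, as illustration only.** Let c be the share of usual-care patients exposed and f the fraction of the full effect that each exposed patient gains. Both are assumptions. The arm difference is multiplied by (1 − cf) and the information by (1 − cf)². For power, assume 90 per arm, two-sided 5% alpha, no dropout, and the standardized effect that gives 80% power: (1.960 + 0.842) × √(2/90) = 0.418. Power is then Φ(0.418 × (1 − cf) × √(90/2) − 1.960), and the total needed to return to 80% is 180/(1 − cf)².

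| cf | Effect left | Information left | Power | Total for 80% |
|---|---|---|---|---|
| 0 | 100% | 100% | 80% | 180 |
| 0.25 | 75% | 56% | 56% | 320 |
| 0.50 | 50% | 25% | 29% | 720 |
| 0.75 | 25% | 6% | 10% | 2880 |

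Only the product matters. Half the controls exposed with half the benefit (0.50 × 0.50 = 0.25) gives the same row as a quarter exposed with the full benefit. At cf = 1 no contrast remains.

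**The case against.** The strongest reply is that the body settles the matter. Sections 2a and 5a both tie the LHW to the intervention arm, and the Appendix can be read as the LHW's manual for patients already in the program; it speaks of pilot patients as a distinct group. Its title names a Stanford, CareMore and Oncology Institute quality improvement pilot and does not mention Unite Here Health. It uses a CareMore referral portal, different eligibility, and surveys at enrollment and 5 months, where the body has baseline, 6 and 12 months. All this suggests text carried over from another program.

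Much of this stands. It makes intended contamination unlikely and points to an Appendix that was not adapted to this trial. It does not remove the conflict, because nothing says that the Appendix is a manual for one arm or a leftover, and it is attached as the patient procedures.

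A reader might infer more: that the protocol plans to treat controls, that every usual-care patient would receive the whole intervention, or that a given share of power is lost. The documents support none of these. The body keeps the LHW to one arm, the Appendix criteria are narrower than trial eligibility, clear overlap is limited to symptom assessment with a case for the support linkage, and no exposure rate or effect of a call is given.

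**Conclusion.** The contradiction is real and rests on the plain wording of both parts. The consequence is conditional: if Appendix 1 is applied as written, usual-care patients who meet its criteria would receive LHW symptom assessment and palliative and support linkage, possibly before allocation, and the difference in ESAS at 12 months would be diluted. The size cannot be estimated from the documents. The range in the table depends on assumed values of exposure and benefit and on an assumed effect and standard design inputs; it shows how quickly a contrast can erode, not what this trial would lose. The point should still be settled, because the correction is cheap and dilution in a randomized contrast cannot be repaired after the fact.

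**What to change.** Amend the protocol as follows.

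- State at the head of Appendix 1 that its LHW procedures apply only after randomization and only to patients allocated to the intervention. Change the wording on inclusion in the program and on calling all patients who meet the criteria so that both refer to patients randomized to the intervention.
- Keep the first call with the Unite Here Health staff named in Section 2a.
- State that ESAS as an outcome, at baseline and 12 months, is collected in both arms and separately from the LHW's ESAS screening. This matters because Section 2a's list of assessments omits ESAS and only the Appendix describes its administration. A blanket ban on ESAS in controls or before randomization could block measurement of the primary endpoint.
- Reconcile the Appendix statement on general treatment education with usual care in Section 2a. Which patients receive it is for the sponsor and investigators to state; no care rule is proposed here.

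The cost is a wording amendment and a staff briefing. It needs no additional patients or staff. If the Appendix proves to be carried-over text, its organizations, eligibility and survey timing also need to be brought into line, which makes the amendment somewhat longer.

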1. PURPOSE OF THE STUDY

a. Brief Summary

The purpose of the LEAPS program is to understand how a trained lay health worker who engages with newly diagnosed patients after a diagnosis of an advanced stage of cancer can help to improve patient satisfaction with their decision-making, activation, quality of life, and healthcare resource utilization.

b. Objectives

We hope to better understand how to help improve patients' care after a diagnosis of advanced cancer. We want to better understand the influence of a local lay health coach on improving patient's efficacy, quality of life, and satisfaction. We also want to know the impact of the program on healthcare resource utilization (emergency department, hospitalization, hospice utilization).

c. Rationale for Research in Humans

Because this is a novel program focused on helping patients better understand their goals of care, human subjects must be used for this project.

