No payment will be provided.

j. Costs to Participants

No costs will be charged to the participant.

k. Planned Duration of the Study

Patients will be enrolled in the study for a total of 12 months from the date of enrollment. Analysis of participant data in aggregate is estimated to take 8 months.

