- 6) PA will place necessary orders for referrals and notify the treating oncology practitioner via Rabbit e-mail

- ❖ Referrals will be requested via the CareMore Utilization Management Provider Portal

Patient Symptom Complaints/Triages

- When LHW pilot patients contact staff with a symptom related complaint, staff will create and assign a triage message to the appropriate provider per the most up to date Mid-Level Triage schedule

- The oncology PA will then assess and treat the patient's symptoms per the symptom management algorithms provided to them
- PA will follow each triage message to ensure that the treating oncology practitioner is following all LHW protocols

After Hour Calls

- When a patient contacts exchange after hours (between 5pm-8:30am Monday-Friday and all day Saturday/Sunday), the on-call treating oncology provider will be paged per the standing protocol.
- All patients will be instructed to identify themselves as pilot program patients to both the exchange service as well as to the treating oncology provider who takes the call.
- The treating oncology provider will assess and treat the patient's symptoms per the symptom management algorithms
- If the treating oncology provider feels that patient requires urgent evaluation which cannot wait until business hours, patient will be referred to the nearest emergency department.
- The treating oncology provider is required to notify the PA about the call on the next business day. The message to the PA will include the reason for call, recommended treatment and outcome.
- PA will ensure that the treating oncology provider has followed symptom management algorithms
- PA will recommend more aggressive symptom management to the treating oncology practitioner if applicable.

Patient Satisfaction, Mental and Emotional Health

- All Surveys are to be done by research team and will be conducted when patients enroll and again 5-months post enrollment

No Shows

- If a patient is a no show to his/her office visit appointment LHW will contact the patient 3 times (1 time per week) in an effort to reschedule patient's appointment
- In the event the LHW is unable to reach patient/reschedule patient's appointment, LHW will send an Outlook e-mail to PA/[name]/[name]/Caremore

Exit Criteria

- ❖ Patient Preference

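### Appendix 1 sets all surveys at enrollment and 5 months, Sections 2a and 5a set them at baseline, 6 and 12 months, and no text says which governs

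*Protocol*

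**What the plan says.** Section 2a gives the survey schedule for the trial. "The Unite Here Health staff, as part of their usual assessments, will conduct the following assessments", it begins, and it then sets them "for patients enrolled in the intervention and the usual oncology care arm at time of randomization and at 6 and 12 months after enrollment". The instruments are the satisfaction with decision-making survey, the patient activation measure (PAM) and the FACT-G quality of life survey.

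Section 5a repeats the schedule: "All patients in the study will receive 3 surveys at baseline, 6 and 12 months after study enrollment". It lists the same three constructs.

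Section 4k sets the length of participation: "Patients will be enrolled in the study for a total of 12 months from the date of enrollment".

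Appendix 1, under its subheading on patient satisfaction and mental and emotional health, has a different rule: "All Surveys are to be done by research team and will be conducted when patients enroll and again 5-months post enrollment". It names no instruments and no later survey.

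The appendix is attached under the title "Appendix 1: Patient Procedures". The line below that title names a CareMore and Oncology Institute project, a "Lay Health Worker Symptom Assessment Quality Improvement Pilot". The body of the protocol names Unite Here Health as the site and mentions neither of those organizations.

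**The concern.** The protocol contains two operative survey schedules that agree only on the first survey. No sentence ranks the body above the appendix, limits the appendix line to other surveys, or marks the appendix as background. Staff who work from the procedures appendix would find a single follow-up survey at 5 months and nothing at 6 or 12.

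The three instruments carry much of the trial's stated purpose, which is to learn whether the program can "improve patient satisfaction with their decision-making, activation, quality of life, and healthcare resource utilization". They measure the first three of those four outcomes. The fourth, utilization, comes from claims data and is not touched by the survey line.

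Two consequences are possible, depending on whom the line is taken to cover. If it covers everyone, both arms lose the 12-month round. If it covers only patients with a lay health worker, the arms are surveyed at different times. A difference between arms at the first follow-up would then be mixed with a one-month difference in timing, and there would be no intervention data to set against usual care at 12 months. A later analysis plan cannot recover a survey that was never taken.

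**Working it through.** The protocol states no figure to reproduce here. The check compares the schedules and then counts surveys.

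**Schedules side by side**

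| Source | Survey times (months) | Patients | Assessor |
|---|---|---|---|
| Section 2a | 0, 6, 12 | both arms | Unite Here Health staff |
| Section 5a | 0, 6, 12 | all patients | not stated |
| Appendix 1 | 0, 5 | not stated in the line; the appendix describes lay health worker pilot patients | research team |

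The only shared time is 0. The first follow-up differs by 6 − 5 = 1 month. The appendix has no 12-month survey. Its last survey leaves 12 − 5 = 7 of 12 months (58%) without survey data.

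**Inputs for the count.** There are 180 patients (Section 4a) and 3 instruments (Sections 2a and 5a). All counts are before death or dropout, and all assume that the appendix line covers these three instruments.

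- Body schedule: 3 instruments × 3 times × 180 = 1,620 surveys, of which 3 × 180 = 540 are at 12 months.
- **Case A, the line is followed for all patients.** 3 × 2 × 180 = 1,080 surveys. Not taken: 1,620 − 1,080 = 540, the whole 12-month round, or 540/1,620 = 33% of the plan. A further 540 surveys move from month 6 to month 5.
- **Case B, the line is followed only for intervention patients.** Section 2a assigns a lay health worker only to that arm. Surveys not taken at 12 months = 3 × intervention-arm size. The protocol gives no allocation ratio. Under an assumed 1:1 split the arm has 180/2 = 90 patients, so 3 × 90 = 270 surveys are not taken. For a range, an assumed 1:2 split (60 intervention patients) gives 180 and an assumed 2:1 split (120) gives 360.
- **Case C, the body schedule is followed for all patients.** None are lost.

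The count understates the damage in Case B. Intervention patients would be surveyed at {0, 5} and usual-care patients at {0, 6, 12}, so the arms share no time after baseline. The 12-month surveys still taken in usual care (270 under 1:1) would have no counterpart.

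The protocol gives no 12-month completion rate, so 540 and 270 are ceilings. If only 50% of patients could still be surveyed at 12 months (an assumption), they halve to 270 and 135.

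**The case against.** The strongest reply is that the body obviously prevails. Two sections agree with each other and fit the 12-month enrollment, while the appendix is headed as another program's pilot. The appendix also describes a different population (stage 3 or 4 or hematologic malignancy, against any cancer diagnosis in Section 4) and relies on systems that the body never mentions. Few readers would let one line in it override Sections 2a and 5a. This is probably the intent, and it lowers the practical risk. It does not settle the conflict: the appendix is attached as this protocol's patient procedures without a disclaimer, and it is the only detailed operating text for the lay health worker.

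A second reply is that the line may mean other surveys. It names no instrument, its subheading does not mention activation, and the appendix elsewhere refers to PHQ-9, which is not among the body's three surveys. This stands as a limit on the consequences, because coverage of the three instruments is an assumption. But the line says all surveys and makes no exception.

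Three stronger readings are tempting, and the documents do not support them.

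- *The 12-month primary endpoint is lost.* The primary endpoint is ESAS (Section 2g), which is not one of these three surveys. Appendix 1 treats ESAS under its own subheading. How ESAS is collected at 12 months is a separate question and forms no part of this point.
- *540 surveys will be lost.* That figure requires the line to be followed for all 180 patients and to cover all three instruments. The appendix describes lay health worker pilot patients, so an effect confined to one arm is at least as plausible.
- *The assessors conflict.* Section 2a names Unite Here Health staff and the appendix names the research team. The latter is undefined and may include the former, so this is only a difference in wording.

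**Conclusion.** The contradiction on survey timing is certain and should be corrected. Its consequences are conditional. They require that the appendix line is followed and that it covers the three instruments, and their size depends on which patients the appendix covers. Under those conditions the first follow-up is one month early and at most 3 surveys per affected patient are missed at 12 months: up to 540 for all 180 patients, or about 270 for the intervention arm alone under an assumed 1:1 split. The second case involves fewer surveys but is the more awkward, because it creates a timing difference between arms and removes the 12-month comparison for satisfaction with decision-making, activation and quality of life. If the body schedule is followed throughout, nothing is lost.

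The practical risk is moderate at most. The point matters because the line is an operative scheduling rule and the repair is very cheap.

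**What to change.** In Appendix 1, replace the 5-month survey line with the Section 2a schedule: enrollment, 6 months and 12 months, in both arms, by the assessors named in Section 2a. Alternatively, delete the line and refer to Section 2a. In either case add one sentence saying that Section 2a governs survey timing where the appendix differs.

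The cost is one line changed and one sentence added. No assessment is added beyond those that Sections 2a and 5a already promise. For survey timing and assessor, Section 2a itself needs no change. The edit does not resolve the appendix's other differences from the body, nor the separate question of ESAS collection.
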